Study Design	This study will use a Type 1 effectiveness-implementation hybrid design to adapt adherence interventions to improve self-management and maintain VL suppression, and enhance the potential for scale up. A Sequential Multiple Assignment Randomized Trial (SMART) will be utilized to maximize real-world implementation and identify effective sequences of treatments and their cost-benefit ratio. For the sub-study, to collect pilot data on the development and implementation of DBS procedures, this study seeks to conduct a mixed-method analysis to examine suitability, feasibility and acceptability of utilizing DBS to obtain viral load (VL) data.
Primary Objective(s)	
 • Compare Cell Phone Support (CPS) versus Text Messaging (SMS) for youth living with HIV (YLH) who are not virally suppressed. • Understand the benefit of incentives for non-responders, identify how to taper interventions for responders, and describe potential moderators of treatment effect.

PROTOCOL TITLE: ATN 144 SMART

	
 • Study the barriers and facilitators to wide-spread implementation as well as cost-effectiveness of treatment sequences. 
Sub-study: Assess the suitability, feasibility and acceptability of using dried blood spot (DBS) collection to obtain timely data on VL monitoring for human immunodeficiency virus (HIV)-positive youth between 15-24 years old.

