	
medication and participants will text back a confirmatory response. The CPS intervention will occur on weekdays, excluding holidays. The SMS intervention will occur every day. The tapered intervention will occur on two weekdays per week, excluding holidays. Incentives will be added to the intervention for those participants who do not meet viral suppression requirements at 3 months.
 
Sub-study: Project DABS does not implement any interventions.

Study Population
	
The study population will consist of HIV-positive youth (15-24 years old, inclusive) who have: a VL ≥ 200 copies/mL within 12 months prior or self-reported adherence (SRA) $\leq 80\%$ in the past 4 weeks after being on a prescribed ART medication regimen for three months prior to eligibility VL; a cell phone and service plan; and the ability to understand written and spoken English.
 
Sub-study:
 
Youth (15-24 years of age) living with HIV (YLH) who are willing to provide DBS specimens for HIV VL measurement and have the ability to understand written and spoken English.

Sample Size
	
We will enroll 120 HIV-positive youth living with HIV aged 15-24.
 
Sub-study: 50

Study Duration for individual participants
	
The total duration of the study for participants is approximately 12 months for both groups.
 
 • Baseline Assessment • Follow Up Assessment (post baseline) 
 ○ 3-Month Follow Up ○ 6-Month Follow Up ○ 9-Month Follow Up ○ 12-Month Follow Up 
Sub-study: approximately 1 month

Study Specific Abbreviations/ Definitions
	
Adherence Facilitator (AF) Adolescents Medicine Trials Network (ATN) Cell Phone Support (CPS) Cell Phone Support + Incentives (CPS-I) Cell Phone Support Tapered (CPS-T) Sequential Multiple Assignment Randomized Trial (SMART) Text Messaging (SMS) Text Messaging + Incentives (SMS-I) Text Messaging Tapered (SMS-T) Youth living with HIV (YLH) ART – antiretroviral therapy CASI – computer assisted self-interviewing

PROTOCOL TITLE: ATN 144 SMART

	
DBS – dried blood spot HIV – human immunodeficiency virus PI – principal investigator VL – viral load

--	--

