1.0 Objectives*

Specific Aims:

1. To compare CPS versus SMS for youth living with HIV who are not virally suppressed.
2. To understand the benefit of incentives for non-responders, identify how to taper interventions for responders, and describe potential moderators of treatment effect.
3. To study the barriers and facilitators to wide-spread implementation as well as cost-effectiveness of treatment sequences.

Secondary Aims:

1. Conduct an exploratory evaluation of tapering the intensity of CPS and SMS (among responders) vs. termination after completion of the 3-6 month intervention to determine if this improves the durability of intervention effects.
2. Explore the relative effectiveness and cost-effectiveness of the individual intervention sequences embedded within the SMART design for responders and non-responders.
3. Assess the Five Components of the Self-management Model and how these components vary over time, are directly improved by the interventions, and mediate intervention effects.
4. Assess barriers and facilitators to the implementation and sustainment of centralized national recruitment, enrollment, intervention delivery, and retention using mixed methods (EPIS surveys, qualitative interviews, fidelity measurements and sequential analysis).

The proposed project is highly innovative because it focuses on a critical area for intervention, adherence to ART in YLH, and goes beyond what has been done previously in several key ways:

1. It directly compares two successful, potentially sustainable, and youth-friendly modes of mobile health (mHealth) youth adherence intervention delivery.
2. The project uses a SMART design to explore a number of key issues surrounding sequencing mHealth interventions in a cost effective manner that would be practical in clinical settings.
3. The CPS intervention uniquely addresses multiple barriers to antiretroviral therapy (ART) adherence in real-time using a social support framework.
4. The study will explore the clinical and public health costs of sequencing of interventions based on viral suppression and sexual transmission risk.

Sub-Study:

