On each call, AFs will assess if the participant has taken their medication for that day and if medication was taken during days when calls to participants are not completed (i.e., weekends and holidays). If the participant has not yet taken their ART medication(s), the AFs will wait for the participant to retrieve and take their medication, if available. If the participant usually takes their ART the night before, then the AF will not request that the participant take their medication during the call. If the participant is non-adherent, the AFs will assess reasons for non-adherence and will engage the participant in brief problem solving around these identified barriers. The AFs will also discuss any new or ongoing problems in the participant's life (e.g., related to housing, transportation, or food), and provide support around problem-solving to address these issues. In addition, they will reinforce prioritizing medications, remind participants about scheduled appointments, and suggest scheduling any relevant referrals (e.g., case management, mental health services, substance use counseling) through their healthcare providers. Youth needing more intensive assistance will be referred to their care team using the information provided on the participant's locator form, and with the youth's permission, the AF will contact the care team to share the concerns.

Text Message Support. Participants enrolled in the SMS intervention will receive daily personalized SMS adherence reminders for three months. Participants will be able to choose the timing and the wording of the text message. Participants will be asked to text back if they did or did not take their ART medications. The texts will be sent through Trumpia, a robust, customizable technology to deliver text messages to participants and track their responses. Trumpia is compliant with HIPAA laws as all personal identifiable data are encrypted.

Incentives and Tapering. After three months of either the CPS or SMS intervention, participants will be sorted into new intervention arms depending on their VL. Participants

PROTOCOL TITLE: ATN 144 SMART

will submit proof of VL and complete a computerized survey. Participants whose VL is <200 copies/mL are categorized as “responders,” because they were able to successfully reduce their VL by adhering to their ART medication during the past three months. Participants whose VL is ≥ 200 copies/mL are categorized as “non-responders.”

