5.0 Procedures Involved*

Enrollment Procedures. Enrollment in this study may occur at any time during the recruitment period. Potential participants recruited utilizing the OneFlorida Data Trust will receive a “text-in” number, in which interested persons will be able to text-in to receive instructions for screening and enrollment. Potential participants through the OneFlorida Data Trust who do not “opt-out” of being contacted could also be directly contacted by the study team to be informed of the study and screening/enrollment options for preliminary eligibility.

Screening and enrollment may occur on the same day, as long as the appropriate VL and ART regimen data are appropriately obtained. If a participant is determined to be eligible for the study, a unique Qualtrics link will be sent to the participant for submitting proof of HIV VL ≥ 200 copies/mL and ART regimen. After final eligibility is determined, study staff sends the potential participant the SMART enrollment link, which contains the study

PROTOCOL TITLE: ATN 144 SMART

consent/assent form, HIPAA Authorization form, and the baseline web-based survey. These are programmed in Qualtrics by the REC. The baseline survey can be completed at the participant's convenience (ideally within 14 days before and 28 days after their scheduled assessment date). Upon completion of all portions of the enrollment link, participants are considered enrolled in SMART. Study staff will then randomize and stratify the participants into their respective intervention arms (CPS or SMS) for the first period of the study. Stratification is based on method of contraction: Perinatal vs Behavioral (and other).

Participants randomized to the CPS intervention group will speak with the AF to determine the start day and call time for intervention phone calls. This phone call should be completed within 30 days from entry. Participants randomized to the SMS intervention will speak with the Project Coordinator (PC) to identify the start day, timing, and content of the text messages they will begin receiving daily.

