Participants may submit VL test results from their standard care providers (at both SRV and non-SRV clinics) as long as they were measured using a level of detection of <200 copies/mL or below and the VL collection dates are within 6 months prior to screening or the baseline assessment, and within 2 weeks prior to or 4 weeks after all other study follow-up assessments. VL measurements using a level of detection ≥ 200 copies/mL will not be accepted. If participants have a standard care provider, but no VL test results

PROTOCOL TITLE: ATN 144 SMART

within the required window period, they may request a new VL test from their usual provider and invoice the REC.

If participants decide to obtain a copy of their standard care VL test results, they will be given two choices on how to submit their VL test results. The REC will inform the participant that they may take a picture of their newly obtained standard care VL test result using their personal cell phone and submit the picture through a secure Qualtrics online submission form. Participants may also request their providers directly send their newly obtained lab results to the REC. This option may require youth to provide a release of information (ROI) if one is not already in place.

If standard of care results are not available, participants who have access to a clinical SRV, but have not completed a VL test within the required window period may request a new VL test for research purposes. The REC will refer participants to a clinical SRV; participants do not need to be an existing patient or establish care at this clinic in order to complete this study component. This new test will be invoiced to the REC and not billed to the patient's insurance. Clinical care VL measurements can be used as long as they were measured using a level of detection of <200 copies/mL or below. VL measurements using a level of detection ≥ 200 mL will not be accepted. Participants should complete this VL test within 1 month of screening before the baseline assessment, and within 2 weeks of each follow-up assessment. The REC will contact providers to submit VL measurements via fax or Qualtrics.

Participants who cannot or do not wish to visit a medical provider may be referred to local Quest Diagnostics labs for VL testing. The REC will order and pay for these labs, and receive VL data directly via online.

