9.0 Subject Population*

Inclusion Criteria. To be considered eligible for enrollment, an individual must meet the following criteria:

- A youth living with HIV (ages 15 years and zero days through 24 years and 364 days, inclusive, at the time of signed informed consent or assent) ;
- Willing to provide proof of VL ≥ 200 copies/mL or blood specimens for HIV VL measurement within 12 months prior to baseline enrollment or self-reported adherence (SRA) $\leq 80\%$ in the past 4 weeks;
- Prescribed an ART medication regimen for a minimum of 3 months prior to eligibility VL;
- The sole owner of a device capable of sending and receiving calls and text messages;
- Able to provide consent for research team to communicate with participant's HIV care provider team

Exclusion Criteria. Exclusionary criteria includes:

- Participants whose mental, physical or emotional capacity does not permit them to complete the protocol as written;
- Inability to understand written or spoken English;
- Concurrent participant in any behavioral research intervention designed to impact medication or care adherence, as indicated in screener.

We will include individuals who are not yet adults:

Study procedures involve no more than minimal risk. The nature and scope of the proposed research study, communication skills training and the CHTC intervention do not pose more than "minimal risk" to participants as defined in 45 CFR Part 46.102, "the probability and magnitude of harm or discomfort anticipated in the research are not greater in and of themselves than those ordinarily encountered in daily life or during the performance of routine physical or psychological examinations or tests".

PROTOCOL TITLE: ATN 144 SMART

We will not include individuals who are adults unable to consent, pregnant women, and prisoners.

Sub-Study:

Inclusion Criteria. This study will include individuals who are not yet adults and pregnant women. Subjects must meet the following study criteria:

- YLH ages 15-24.
- Willing to provide DBS specimens for HIV viral load measurements.
- Living in the U.S.

Exclusion Criteria. This study will exclude prisoners and those who are unable to consent. This sub-study also excludes subjects that meet the following criteria:

- Subjects whose mental, physical or emotional capacity does not permit them to complete the protocol as written.
- Inability to understand written or spoken English.
- Subjects with hemophilia or on anti-coagulation therapy.

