13.0 Withdrawal of Subjects*

Criteria for Premature Discontinuation

These are the categories of "dropping" participants along with their definitions.

PROTOCOL TITLE: ATN 144 SMART

Category: Definition	Procedure	Notes

Ineligible prior to BL (Prior to Consent):
 
Screened eligible, but finally ineligible after proof of suppressed viral load (VL) test result within the past 12 months due to necessary VL eligibility confirmation
	
Remove from reminder call lists and mark as “Do Not Contact” in Access.
	
Counted towards screened number only.

Refused baseline (BL) (Prior to Consent):
 
Screened eligible, but never provided consent during BL assessment and/or no longer wishes to be contacted.
	
Remove from reminder call lists and mark as “Do Not Contact” in Access.
	
Counted towards screened number only.

Withdrew during BL (After Consent): Provided consent but refused to finish BL assessment.
	
Remove from reminder call lists and mark as “Do Not Contact” in Access.
	
Counted up to and including magic number; these participants get marked as “Withdrew from Study” for IRB purposes.

Withdrew after BL (After Consent): Participant completed the BL but asked to be removed from the study thereafter.
	
Remove from Follow-Up Call Lists; should be Tracked as enrolled and have a condition assigned.
	
Counted up to and including randomized/enrolled and stays in all denominators for Follow-Up retention; these participants get marked as “Withdrew from Study” for IRB purposes.

Ineligible after BL (After Consent): Participant either completed the BL OR both BL and follow-ups but was found ineligible for enrollment at a later date (e.g., found to have psychiatric conditions while collecting BL data)
	
Remove from Follow-Up Call Lists; should be Tracked as enrolled and have a condition assigned
	
Counted up to and including randomized/enrolled and stays in all denominators for Follow-Up retention; these participants get marked as “Withdrew from Study” for IRB purposes.

Refused intervention (if applicable), Still Enrolled: Participants who are no longer interested in the intervention, but have
	
Remain in Database to be called for Follow-Up visits
	
Treated as other enrolled participants except they wouldn't receive any future randomization or intervention.

indicated a willingness to continue to be followed for Follow-Up Visits		

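### Entry rules disagree on whether virally suppressed youth may enroll, and month-3 suppression is described as a reduction in viral load whatever the baseline value

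*Protocol*

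**What the plan says.** On entry, the Protocol points two ways.

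- Study Summary, Study Population: VL of at least 200 "copies/mL within 12 months prior or self-reported adherence (SRA") at or below 80% over four weeks.
- Section 9.0: willingness to provide proof of VL of at least 200 or "blood specimens for HIV VL measurement within 12 months prior to baseline enrollment or self-reported adherence (SRA"), with the same 80% cut-off. The SRA route has no VL floor.
- Section 5.0, Enrollment Procedures: once a youth is found eligible, "a unique Qualtrics link will be sent to the participant for submitting proof of HIV VL" of 200 or more. No separate branch is given for the SRA route.
- Section 13.0 lists a pre-baseline category: "Screened eligible, but finally ineligible after proof of suppressed viral load (VL) test result within the past 12 months".
- Section 1.0, first specific aim: "To compare CPS versus SMS for youth living with HIV who are not virally suppressed".

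A qualifying VL need not be recent. It may be up to 12 months old under section 9.0, and a provider result used for baseline is acceptable if its "collection dates are within 6 months prior to screening or the baseline assessment" (section 5.0).

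On response, section 4.0 classes everyone with month-3 VL below 200 as a responder, "because they were able to successfully reduce their VL by adhering to their ART medication during the past three months". Baseline VL plays no part.

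On analysis, first-stage randomization is stratified by mode of infection only (Protocol 5.0 and 16.0; SAP 1.1). Other baseline variables become covariates only if they are imbalanced and also correlate above 0.30 with the outcome.

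**The concern.** The conflict leaves the trial population undefined. A report could not say whether the randomized set matches the first aim, and staff applying different sections would reach different decisions on the same person.

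If the SRA route operates, or an old VL qualifies someone who has since been suppressed, some participants may be below 200 at randomization. That has two consequences. They can be counted as responders with no change in VL, and they then enter the tapering-versus-termination randomization, whose purpose is to study durability of an intervention effect. They may also add similar success rates to both arms and so shrink the CPS-SMS difference in VL suppression. The same applies to outcomes built partly on VL: the VL-then-SRA composite in SAP 1.2, and the exploratory either/or composite in SAP 1.2.1, on which a suppressed entrant already scores 1.

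Nothing in the plan reliably deals with this. Baseline suppression that happens to be balanced between arms would never be adjusted for under the covariate rule.

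**Working it through.** **1. Two youths under each section**

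| Youth | Study Summary and 9.0 | 5.0 Enrollment | 13.0 |
|---|---|---|---|
| A: VL below 200, SRA 70% | Eligible by SRA | Cannot supply the proof requested | Ineligible before baseline |
| B: VL at least 200 ten months ago, below 200 last month | Eligible by VL | Can supply the older result | Ineligible once the recent result is shown |

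Both get opposite answers. This step needs no assumption.

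**2. The plan's own power figure**

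SAP 1.2.4 uses effect size 0.55, two-sided alpha 0.05, 80% power and 10% attrition. Per arm, n = 2(1.960 + 0.842)²/0.55² = 2 × 7.85/0.3025 = 51.9, rounded up to 52. The total is 104, and 104/0.9 = 115.6, rounded up to 116. This matches the SAP row for a responder rate of 0.5. With 60 × 0.9 = 54 per arm, power is 0.81 (noncentral t). The figure reproduces. It has no term for participants already suppressed.

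**3. Illustration of dilution**

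The documents do not give the share s suppressed at entry, so every input here except n is an assumption: s = 10%, 20% or 40%; month-3 suppression of 60% (CPS) and 35% (SMS) in those unsuppressed at entry; 85% of the already suppressed staying so in both arms; 54 analysed per arm.

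- Arm rate: p = 0.85s + (1 − s) × 0.60 for CPS, and 0.85s + (1 − s) × 0.35 for SMS.
- Arcsine effect: h = 2·arcsin√p(CPS) − 2·arcsin√p(SMS).
- Power: Φ(h√(54/2) − 1.96). At s = 0, h = 0.506, giving Φ(0.67) = 75%.
- Share of responders already suppressed: 0.85s divided by the mean of the two arm rates.

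| s | CPS | SMS | Difference | Power | Share of responders |
|---|---|---|---|---|---|
| 0 | 60% | 35% | 25 points | 75% | 0 |
| 10% | 62.5% | 40% | 22.5 points | 66% | 17% |
| 20% | 65% | 45% | 20 points | 56% | 31% |
| 40% | 70% | 55% | 15 points | 37% | 54% |

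At s = 5%, power is 70%. Setting maintenance at 75% or 95% in both arms moves power by less than 2 points.

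A second model applies the SAP's effect size with complete maintenance in both arms, so the effect becomes 0.55(1 − s). Power falls from 0.81 to 0.72, 0.62 and 0.51 at s = 10%, 20% and 30%.

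**4. What if CPS also helps youth stay suppressed?**

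The last column restricts the test to baseline VL of at least 200, with 54(1 − s) per arm.

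| s | Full set, 85% vs 85% | Full set, 85% vs 75% | Full set, 85% vs 65% | Baseline VL at least 200 only |
|---|---|---|---|---|
| 10% | 66% | 69% | 73% | 70% |
| 20% | 56% | 64% | 71% | 65% |
| 40% | 37% | 53% | 69% | 53% |

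At 85% vs 75% the full set does about as well as the restricted set. At 85% vs 65% it does better and loses little against 75%.

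**The case against.** A reader might infer that suppressed youth were in fact enrolled and that the primary contrast has lost up to half its power. The documents do not support that.

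- **Entry.** The aims, the proof-of-VL step and the discontinuation table all point to an unsuppressed population. So do section 2.0, which mentions youth ineligible on self-reported VL, and the sub-study text in 5.0, which offers referral only to those with VL of at least 200. The share could be near zero. This stands, but it does not remove the contrary text in the formal inclusion criteria or the age allowed for a qualifying VL.
- **Test.** The decision rule in Protocol 16.0 and SAP 1.2.1 is the group-by-time interaction in a linear mixed model that includes baseline, and 16.0 also compares the fall in log10 VL. The SAP moves the primary outcome to SRA or a VL/SRA composite, with a week-48 endpoint. A group with flat trajectories could dilute a slope contrast too, but the figures above do not measure it. This stands.
- **Restricting the main analysis.** It is tempting to make those with baseline VL of at least 200 the main comparison. Step 4 shows that the gain depends on equal maintenance, and section 3.0 names maintaining suppression as a goal. It would also displace the full intention-to-treat set.
- **SRA as a mirror image.** A youth entering on VL may report SRA above 80%. The SAP states no SRA success cut-off, so such a youth cannot be called already successful.
- **Blood specimens.** Reading section 9.0 as admitting anyone willing to give blood is strained, since the Study Summary states the threshold.
- **Tapering.** That comparison is exploratory and unpowered, and it remains randomized among youth suppressed at month 3. The fault is one of description. The responder shares in step 3 are also somewhat high, because section 5.0 counts a missing month-3 VL as non-response.

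**Conclusion.** The contradiction on entry is certain from the text alone, and so is the fault in the responder description: month-3 VL below 200 does not show a reduction in anyone suppressed at entry. Dilution is conditional. It needs suppressed youth to have entered and both arms to maintain suppression about equally. Under those assumptions, power of a month-3 chi-square test on VL suppression falls from 75% to 66%, 56% and 37% at shares of 10%, 20% and 40%. With a share near zero, or better maintenance under CPS, the loss from including these youth is small or absent. No size can be given for the mixed model, SRA or the composite. The point should be fixed before analysis, but it does not invalidate the randomized comparison.

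**What to change.** 1. Reconcile the Study Summary and Protocol 9.0 with sections 5.0 and 13.0 so that one entry rule applies. State how a more recent suppressed result bears on an older qualifying one. Report baseline VL status and entry route by arm.
2. In SAP 1.2.1, keep the full intention-to-treat set as the main comparison. Stratify or adjust the stage-1 comparison of VL suppression, and of the VL/SRA composite, by baseline VL status (below 200 or not) or entry route, whether or not imbalance is seen. Where baseline VL is already an outcome in the mixed model, entry route is the cleaner term. Add a category for missing baseline VL. Pre-specify a supporting analysis in those with baseline VL of at least 200, the population of the first aim.
3. Describe responders in Protocol 4.0 as suppressed at month 3. If tapering versus termination is reported, show those who went from 200 or more to below 200 separately from those who maintained suppression. SAP 1.2.2 now bases early response on SRA, so the label should name the measure used.

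The cost is wording, one model term and a small supporting analysis, using values planned for collection at baseline. Adjustment does not undo dilution, and the supporting analysis has fewer participants. A baseline VL may be months old, so some misclassification remains.
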